17. VULNERABLE POPULATION

As described in the exclusion criteria, no vulnerable population will be included in this trial.

18. SUSPENSION OR PREMATURE TERMINATION OF THE CLINICAL

INVESTIGATION

Vanderbilt University Medical Center may suspend or prematurely terminate either a clinical investigation or an individual investigation site or the entire clinical investigation for significant and documented reasons. A Principal Investigator, IRB, or regulatory authority may suspend or prematurely terminate participation in a clinical investigation at the investigation sites for which they are responsible. If suspicion of an unacceptable risk to subjects arises during the clinical investigation, or when so instructed by the IRB or regulatory authorities, Vanderbilt University Medical Center shall suspend the clinical investigation while the risk is assessed. Vanderbilt University Medical Center shall terminate the clinical investigation if an unacceptable risk is confirmed.

Vanderbilt University Medical Center shall consider terminating or suspending the participation of a particular investigation site or investigator in the clinical investigation if monitoring or auditing identifies serious or repeated deviations on the part of an investigator. If suspension or premature termination occurs, the terminating party shall justify its decision in writing and promptly inform the other parties with whom they are in direct communication. The Principal Investigator and Vanderbilt University Medical Center shall keep each other informed of any communication received from either the IRB or the regulatory authority.

If, for any reason, Vanderbilt University Medical Center suspends or prematurely terminates the investigation at an individual investigation site, Vanderbilt University Medical Center shall inform the responsible regulatory authority as appropriate and ensure that the IRB is notified, by the Principal Investigator or designee. If the suspension or premature termination was in the interest of safety, Vanderbilt University Medical Center shall inform all other Principal Investigators.

If suspension or premature termination occurs,

- Vanderbilt University Medical Center shall remain responsible for providing resources to fulfill the obligations from the protocol and existing agreements for following up the subjects enrolled in the clinical investigation, and
- The Principal Investigator or authorized designee shall promptly inform the enrolled subjects at his/her investigation site, if appropriate.

When Vanderbilt University Medical Center concludes an analysis of the reason(s) for the suspension, implements the necessary corrective actions and decides to lift the temporary suspension, Vanderbilt University Medical Center shall inform the Principal Investigators, the IRBs, and, where appropriate, the regulatory authority of the rationale and provide them with the relevant data supporting this decision.

Concurrence shall be obtained from the IRBs and, where appropriate, regulatory authorities before the clinical investigation resumes. If subjects have been informed of the suspension, the Principal Investigator or authorized designee shall inform them of the reasons for resumption.

19. PUBLICATION POLICY

The results of the clinical investigation will be made publicly available in case of positive or negative results following the completion of the trial.

Appendix A: Performance Status Criteria ECOG Performance Status Scale

ECOG Performance Status Scale		Karnofsky Performance Scale	
Grade	Descriptions	Percent	Description
0	Normal activity. Fully active, able to carry on all pre-disease performance without restriction.	100	Normal, no complaints, no evidence of disease.
		90	Able to carry on normal activity; minor signs or symptoms of disease.
1	Symptoms, but ambulatory. Restricted in physically strenuous activity, but ambulatory and able to carry out work of a light or sedentary nature (e.g., light housework, office work).	80	Normal activity with effort; some signs or symptoms of disease.
		70	Cares for self, unable to carry on normal activity or to do active work.
2	In bed <50% of the time. Ambulatory and capable of all self-care, but unable to carry out any work activities. Up and about more than 50% of waking hours.	60	Requires occasional assistance, but is able to care for most of his/her needs.
		50	Requires considerable assistance and frequent medical care.
3	In bed >50% of the time. Capable of only limited self-care, confined to bed or chair more than 50% of waking hours.	40	Disabled, requires special care and assistance.
		30	Severely disabled, hospitalization indicated. Death not imminent.
4	100% bedridden. Completely disabled. Cannot carry on any self-care. Totally confined to bed or chair.	20	Very sick, hospitalization indicated. Death not imminent.
		10	Moribund, fatal processes progressing rapidly.
5	Dead.	0	Dead.

Appendix B: Neurocognitive Function

According to Meyers and Brown (Meyers CA 2006), for a neurocognitive test battery to be useful in clinical research it should fulfill the following 6 criteria:

- a) It should be brief in order to reduce patient and clinical burden.
- b) It should have alternate forms of the tests in order to reduce practice effects and therefore allow for repeated test administration.
- c) It should have good psychometric properties such as validity, reliability, and population norms so that true changes in NCF above fluctuations due to situational factors can be detected.
- d) It should be sensitive to changes in cognitive function.
- e) It should be highly standardized and easy to administer so that no specialized psychological training is necessary in order to be able to administer the test battery.
- f) Most patients should be able to complete the neurocognitive tests, even patients with significant neurocognitive problems, in order to reduce the likelihood of selection bias.

See Statistical Considerations chapter for further information regarding the evaluation of neurocognitive endpoints

Test Battery for Neurocognitive Function

Neurocognitive Parameter Measured	Test	Time to Administer (Minutes)
Auditory/verbal learning and memory	Hopkins Verbal Learning Test-Revised	5
Visual-Motor Scanning Speed	Trail Making Test Part A	5
Executive Function	Trail Making Test Part B	5
Verbal Fluency	Controlled Oral Word Association Test	5
	Total Time	20

Prior to initiation of TTFs, all patients will undergo baseline neurocognitive testing using these neurocognitive instruments. At that time, history regarding level of education reached will also be obtained. After completion of therapy, all patients will undergo this neurocognitive test battery, conducted by trained and certified nurses or clinical research associates, every 8 weeks until death or until one year after therapy, whichever comes first. In the analysis of neurocognitive decline, each patient will serve as his/her own control, as decline for each neurocognitive test at each follow-up time point will be compared to baseline.

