6. DESIGN OF THE CLINICAL INVESTIGATION

1. General

a) Description of the Type of Clinical Investigation to be Performed

This is a prospective, single-arm, open-label multicenter pilot study. All patients will undergo TTFs using the NovoTTF-200A System set to an output frequency of 200 kHz. Patients on the study may receive chest irradiation at the discretion of the treating physician. Moreover, should the patient develop progressive extracranial disease, then the patient may receive systemic therapy at the discretion of the treating physician. All oncology therapies will be recorded in the clinical trial record.

NovoTTF-200A will be discontinued in patients who develop intracranial failure while on therapy. All patients who develop intracranial failure may undergo WBRT or best supportive care at the discretion of the treating physician.

All study follow-up procedures should continue according to the study's protocol until death, or until one of the other criteria for removal from the study is met (see **Section 3.C** below).

b) Outcome Measures

Primary Outcome Measure:

Feasibility, as measured by tolerability of TTFs, will be recorded as percentage of patients continuing TTF therapy until intracranial tumor progression, discontinuation due to DLT, or continuation of therapy for at least 6 months.

Secondary Outcome Measures:

1. Time to intracranial failure, as measured from date of starting NovoTTF-200A to intracranial failure as a first event. Death prior to evidence of intracranial failure is treated as a competing risk and will be censored on the time to intracranial failure curves.
2. Overall survival, defined from the date of starting NovoTTF-200A to death, or censored at the date of last follow-up.
3. Rate of intracranial failure at 2, 4, 6, 8, 10, 12 months after starting NovoTTF-200A
4. Intracranial failure free survival, defined from the date of starting NovoTTF-200A to the first intracranial failure or death (whichever occurs first) or, otherwise, censored at the last MRI imaging assessment date on which the patient was reported alive without intracranial failure.
5. Rate of decline in cognitive function as measured by HVLT-R free recall, delayed recall, and delayed recognition; COWAT; and TMT Parts A and B at 2, 4, 6, 8, 10, 12 months follow-up.
6. Time to neurocognitive failure, as measured by cognitive decline on a battery of tests: HVLT-R free recall, delayed recall, and delayed recognition; COWAT; and TMT Parts A and B.

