The same slice thickness and contrast material type & dose should be maintained throughout the entire study. The NovoTTF-200A System and all components including the transducer arrays must be removed and cannot be brought into the MR environment.

- 10. Device compliance (if applicable)

Once every 8 weeks, for one year or until intracranial failure (whichever comes first) the following

neurocognitive tests will be performed:

1. HVLt-R
2. TMT Part A and B

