NCCTG N0574, NCCTG N0577, RTOG 0825, ECOG E3F05, NCCTG N0874/ABTC 09-0, and N107C. Assessments will be conducted every 8 weeks for the first year or until intracranial failure, whichever occurs first. The HVLt-R test has been used and validated in multiple prior phase III trials of patients with brain metastases [9, 21]. HVLt-R incorporates 6 different forms, helping to mitigate practice effects of repeated administrations. Each form includes 12 nouns (targets) with 4 words drawn from 3 semantic categories, which differ across the 6 forms. The test involves memorizing a list of 12 targets for 3 consecutive trials (immediate recall), recalling the 12 targets after a 20-minute delay (delayed recall), and identifying the 12 targets from a list of semantically related or unrelated items (delayed recognition). In COWAT [Johnson SC et al, *Clin Neuropsychol.* 2012; 26(7):1230-41, Johnson DR et al, *Neuro Oncol.* 2012;14(6):808-16], the patient produces as many words as possible in 1 minute for a specific letter and the test assesses language and executive/frontal skills. The test is widely used and is part of the Halstead-Reitan Neuropsychological Battery. Impairment in the understanding of language or the motor expression of language will impair the results in this trial. Since such functions are affected by brain-directed therapies such as WBRT, the test could be sensitive to the experimental treatment effects on those functions. TMT [Bowie CR and Harvery PD, *Nat Protoc.* 2006; 1(5):2277-81] is a measure of visuospatial scanning, attention, sequencing and cognitive processing speed (Part A) and executive function (Part B). Those neurocognitive functions could be affected both by brain metastasis and by therapies directed to the brain, and will therefore be used in the trial. Patients must “connect the dots” either in a numbered sequence or alternating letters and numbers.

b) Sample Size Determination: Because the primary endpoint is feasibility, the proposed sample size is not driven by statistical hypotheses. Rather, we propose the sample size of 25 so that we will have precise enough information for planning the next phase of treatment development. The following table summarizes the point estimate and 95% confidence interval when n=25.

# patients continuing therapy	10	15	18	20
Point estimate	40%	60%	72%	80%
95% confidence interval	23% - 59%	41% - 77%	52% - 86%	61% - 91%

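### Cognitive decline is judged only against each patient's own baseline in a single-arm study, with no form order and no allowance for retest gain, so gain can mask decline

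*Combined protocol and SAP*

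**What the plan says.** Appendix B fixes the comparison for the cognitive tests: "each patient will serve as his/her own control, as decline for each neurocognitive test at each follow-up time point will be compared to baseline". Section 6.1(a) fixes the design: "This is a prospective, single-arm, open-label multicenter pilot study".

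The plan does think about practice effects. Section 9(a) says the battery was chosen partly because its practice effects are small and it has published norms, and adds that "HVLt-R incorporates 6 different forms, helping to mitigate practice effects of repeated administrations". Appendix B lists criteria for a useful battery, and criterion (b) reads "It should have alternate forms of the tests in order to reduce practice effects and therefore allow for repeated test administration".

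On COWAT, Section 9(a) says that "the patient produces as many words as possible in 1 minute for a specific letter". It does not mention alternating letter sets. Its account of TMT mentions no alternate versions. No section gives a form order for any test.

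Appendix B refers the reader to the statistics chapter for how the cognitive endpoints are evaluated. Section 9(d) does not name the cognitive tests. It says only that the remaining time-to-event data are handled in the same way as those it has described. Neither place gives a practice correction, a reliable-change rule or a cut-off for neurocognitive failure.

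On timing, Appendix B has "Prior to initiation of TTFs, all patients will undergo baseline neurocognitive testing using these neurocognitive instruments", and Section 9(a) has "Assessments will be conducted every 8 weeks for the first year or until intracranial failure, whichever occurs first".

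**The concern.** Secondary objectives 5 to 7 in Section 5(a) concern cognitive decline, time to neurocognitive failure and neurocognitive failure-free survival. Section 3(e) presents the device as a possible alternative to PCI partly because it might spare late cognitive function.

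A patient who sits the same kind of test repeatedly may score better from familiarity alone. A randomised comparison largely removes this, because both arms gain. With one arm and a plain change from baseline, the gain is added to the true change. A patient who has declined can then look stable, and that error favours the device.

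Form differences are a separate problem. If all patients take the HVLT-R forms in the same sequence, a form that is easier or harder than the baseline form shifts the whole group at that visit. More patients do not average this out.

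**Working it through.** The plan gives no figure on this point. Its only design calculation, the table of intervals at n=25 in Section 9(b), concerns the primary endpoint. It reproduces as a two-sided 95% Wilson interval (10 of 25 gives 23.4% to 59.3%, printed as 23% to 59%) and has no bearing here.

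**1. Which scores have stated alternate forms.** The battery yields six scores: HVLT-R free recall, delayed recall and delayed recognition, COWAT, TMT A and TMT B. Alternate forms are stated for the three HVLT-R scores. None are stated for the other three, at any of the six follow-ups.

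**2. Sittings against forms.** Sections 7(b) and 9(a) give baseline plus weeks 8, 16, 24, 32, 40 and 48, so 1 + 6 = 7 sittings against 6 HVLT-R forms. The shortfall is one form, at the last sitting only. The count depends on which schedule applies. Appendix B places follow-up after therapy and runs it to one year after therapy or death. Appendix C footnote 4 stops at a second cerebral progression. One reading of Appendix B (testing through 6 months of therapy and the year after) gives up to 10 sittings.

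**3. How many patients reach the seventh sitting.** This uses the trials cited in Section 3(a), with survival and intracranial failure taken as independent (an assumption). Expected number = 25 × S(12) × (1 − brain metastasis rate at 12 months).
- EORTC trial, control: 25 × 0.133 × (1 − 0.404) = 2.0
- EORTC trial, PCI: 25 × 0.271 × (1 − 0.146) = 5.8
- Japanese trial, observation: S(12) = 0.5^(12/15.1) = 0.576 (exponential survival assumed), so 25 × 0.576 × (1 − 0.580) = 6.1
- Japanese trial, PCI: S(12) = 0.5^(12/10.1) = 0.439, so 25 × 0.439 × (1 − 0.324) = 7.4

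This is roughly 2 to 7 of 25. Without independence, the bounds from max(0, S − rate) to min(S, 1 − rate) span 0 to 11 across the four arms.

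**4. What retest gain does to a decline count.** Every input here is assumed, because the documents give none. Scores are in baseline SD units, oriented so that a fall is worse. The retest correlation is r, the true decline 0.5, the gain g, and decline is counted at a drop of 1.
- SD of change = √(2(1 − r)) = √(2 × 0.25) = 0.707 at r = 0.75
- Share flagged = Φ((−1 + 0.5 − g) / 0.707)

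| Gain g (SD) | Share flagged |
|---|---|
| 0 | 24.0% |
| 0.2 | 16.1% |
| 0.3 | 12.9% |
| 0.5 | 7.9% |

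Going from g = 0 to g = 0.3, the fall is 28.8% to 18.6% at r = 0.60 and 18.1% to 7.2% at r = 0.85.

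**5. Form shifts.** The same formula covers a form that is harder than baseline by 0.3 SD (g = −0.3): Φ(−0.2 / 0.707) = 39%. The share flagged then rises from 24% to 39%, so the error runs against the device.

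**6. A common shift against the precision of the mean.** The SE of mean change is 0.707/√n. A 0.3 SD shift is 0.3/0.141 = 2.1 SE at n = 25, 0.3/0.224 = 1.3 SE at n = 10, and 0.3/0.316 = 0.9 SE at n = 5. The first figure is a ceiling, because it needs all 25 patients still tested at that visit.

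**The case against.** The strongest reply is that the plan has already dealt with practice effects. It chose the tests partly for this reason, it cites six HVLT-R forms, and the endpoints are secondary in a pilot whose sample size rests on no hypothesis. Section 3(e) makes a phase 2 study conditional on safety and tolerability, not on cognition. All of that stands, and it keeps the point minor. But selecting tests is not the same as instructing sites or adjusting an analysis. Six forms help only if sites rotate them, and up to three institutions have no list to follow.

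Some stronger readings are tempting, and the documents do not support them.
- A reader might infer that form differences also make cognition look preserved. They have no fixed sign: step 5 shows a harder later form creating false decline.
- A reader might infer that the battery fails criterion (b). The plan is silent on alternate COWAT and TMT versions. It does not say that none exist, and the criteria are worded as general guidance. The gap is one of specification.
- A reader might treat seven sittings against six forms as the main fault. It touches only month 12, probably a minority of patients, and a form last used many months before.
- A reader might take 2.1 standard errors, or the fall from 24% to 13%, as the expected bias. Both rest on assumed inputs.

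**Conclusion.** The concern holds in a limited form. Decline is measured only against own baseline in one arm, with no form order, no stated alternate versions for half of the scores, and no allowance for retest gain. Gain can therefore mask decline, in the device's favour. Form differences under a common order add error in either direction.

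The size cannot be derived from the documents. The illustration (24% to 13% flagged for a 0.3 SD gain) shows how sensitive a decline count is, given a retest correlation of 0.75, a true decline of 0.5 SD and a 1 SD cut-off. It does not estimate the actual bias. A more basic gap lies beside it: neurocognitive failure has no cut-off, so objectives 6 and 7 cannot be computed until one is stated. The unadjusted comparison is a weakness under any of the three testing schedules.

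Severity is minor: a cheap improvement to secondary endpoints of a 25-patient feasibility study.

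**What to change.** Amend Appendix B and Section 9 as follows.

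1. Assign the HVLT-R forms in a counterbalanced order, rotating the starting form across patients. If a seventh sitting occurs, reuse the form with the longest gap since its last use.
2. Use alternate COWAT letter sets and TMT versions, where available, rotated in the same way.
3. Beside the raw change from baseline, report a practice-adjusted reliable change: (follow-up − baseline − expected retest change) / SD of retest differences between individuals. The denominator is this between-individual SD, not the standard error of a published mean. State the source of the constants. Do not read the absence of raw decline alone as preserved cognition.
4. Reconcile the testing schedules in Sections 7(b) and 9(a), Appendix B and Appendix C footnote 4.

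The cost is a form-allocation list, a table of retest constants and some wording, with no extra visits or patients. Items 1 and 2 must be set before a patient is tested, because form order cannot be repaired afterwards. The downside is that retest constants come from other populations and intervals, so the adjusted result is approximate and may look less favourable. For that reason it belongs beside the raw change and does not replace it.

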Appendix C: Study Calendar

	T=(-21)-0 Days (Baseline)	T=0 days (Registration to Treatment)	T= 0 to 21 days (Registration to Treatment to 21)	T=every 8 weeks until intracranial failure (Follow-Up) (±7days)	T= 8 weeks from treatment termination (±7days)	T= every 4 weeks from treatment discontinuation (±7 days)
Signed ICF	X					
MRI of brain ¹	X			X	X	
Medical history	X					
Performance Status (KPS score)	X			X	X	
Physical examination ²	X			X	X	
Neurological examination	X			X	X	
Complete blood count including differential	X			X	X	
Serum chemistry panel ³	X			X	X	
Neurocognitive Testing ⁴	X			X		
Quality of Life Questionnaire ⁴	X			X		
Serum pregnancy test ⁵	X					
Blood coagulation test ⁶	X					
Registration to treatment (Start of use of NovoTTF-200A)		X				
Adverse event collection and recording ⁷		X	X	X	X	
Concomitant medication recording	X	X	X	X	X	
Device compliance assessment				X		
Telephone follow-up for survival						X

1. A high resolution, isovolumetric T1-weighted post-gadolinium MRI of the brain using a 3T MR scanner. **Treatment with the NovoTTF-200A System is to begin within 21 days after this baseline MRI.** Additional parameters include:

- FOV: 256 mm x 256 mm
- Matrix: 256x256
- Slice thickness: 1 mm
- Full brain coverage

The same slice thickness should be maintained throughout the study. The NovoTTF-200A System and all components including the transducer arrays must be removed and cannot be brought into the MR environment.

2. Vital signs are included as part of the physical exam
3. Serum chemistry panel includes: BUN, Creatinine, Sodium, Potassium, ALT, AST, Bilirubin
4. Neurocognitive Testing and QOL questionnaire will be performed for one year or until second cerebral progression (whichever comes first)
5. If applicable and within 14 days
6. Coagulation tests include PT, PTT and will be performed as part of the follow up procedures only if clinically indicated
7. Reporting period will begin immediately following registration to treatment (start of use of NovoTTF-200A) and ends at the conclusion of 8 weeks following treatment termination

